#### 1.4. CCR2 Inhibitor CCX140-B: Clinical Experience

CCX140-B has been assessed in 4 Phase 1 clinical trials in healthy volunteers, one Phase 2 trial in subjects with diabetes, and two Phase 2 trials in subjects with diabetic nephropathy. A tabular summary of clinical studies conducted with CCX140-B and submitted to IND 114469 are provided in the Investigator's Brochure.

Efficacy findings in study CL005\_140 in patients with diabetic nephropathy and proteinuria provide support for exploring CCX140-B in FSGS. In that trial, 192 subjects with diabetic nephropathy received uninterrupted dosing for up to 52 weeks with placebo, 5 mg daily of CCX140-B or 10 mg daily of CCX140-B. Compared to placebo, CCX140-B was associated with greater reduction in albuminuria. Specifically, changes from baseline in the ratio of urinary albumin to creatinine (UACR) averaged -2% in the placebo group (95% CI -11% to +9%), -18% in the CCX140-B 5 mg group (95% CI -26% to -8%), and -11% in the CCX140-B 10 mg group (95% CI -20% to -1%). The decrease in UACR was observed at the earliest measured time point (Day 15) and reached a maximum decrease by the Day 85 visit ([de Zeeuw et al., 2015](#)). Of note, subjects entering the study were stratified based on the level of proteinuria at baseline. In a pre-specified subset analysis, the greatest percentage improvement in UACR from baseline was observed in subjects who presented with the highest baseline UACR (801-3000 mg/g) and eGFR of at least 60 mL/min/1.73m^2. In this subset mean changes in UACR from baseline were +45 % in the placebo group (95% CI -6% to +121%, n=8), -23% in the CCX140-B 5 mg group (95% CI -55% to +32%, n=5; p = 0.03 vs control), and -39% in the CCX140-B 10 mg group (95% CI -61% to -7%; n=8; p = 0.004 vs control).

The pathogenic mechanisms that contribute to proteinuria and progressive renal dysfunction in diabetic nephropathy are shared, at least in part, with mechanisms in FSGS ([Jefferson et al., 2008](#)). Specifically, a decrease in podocyte number has been shown in subjects with both type I and type II diabetes mellitus, reduced podocyte number may precede the onset of clinically detectable albuminuria and/or proteinuria by several years, foot process effacement is observed, and experimental and clinical studies have shown a direct correlation between the magnitude of proteinuria and the extent of effacement and decrease in podocyte number. Further, as in FSGS, increased glomerular proteinuria leads to enhanced tubular cell uptake of protein, leading to complement activation, tubulointerstitial inflammation and release of fibrogenic growth factors and inflammatory cytokines.

When taken together with results from the pre-clinical studies, and a favorable clinical safety profile (see Investigator's Brochure), these observations further support evaluation of CCX140-B in highly proteinuric renal diseases, including FSGS.

## 1.5. Rationale for Study in FSGS: Unmet Medical Need

Supportive management for FSGS includes renin-angiotensin aldosterone system inhibitors (RAAS) blockers for management of proteinuria and hypertension when indicated, and statins for management of dyslipidemia. For patients presenting with primary FSGS and proteinuria, glucocorticoids at doses equivalent to 0.3 to 1.5 mg/kg/d prednisone for durations of 4 to 24 months have been reported to achieve complete or partial remission in 28% to 74% of patients (Korbet et al., 1994; Banfi et al., 1991; Cattran and Rao, 1998; Rydel et al., 1995; Gipson et al., 2016; Cattran et al., 2008).

Limitations of current treatment include inadequate response in a significant proportion of patients, frequent recurrence of disease in responders, and progression of renal insufficiency in most patients over time. The most informative published data on rate of progression derives from the Toronto Glomerulonephritis Registry (Cattran et al, 2008). Among 370 patients with FSGS, eGFR declined by 5 to 18 g/ml/1.75m^2/year in the subset with nephrotic level proteinuria. Among patients with high levels of proteinuria at the time of presentation, 50% progressed to ESRD within 3 to 8 years (D'Agati, 2011). In the US, the estimated incidence of newly-recognized FSGS, and the reported incidence end stage renal disease (ESRD) due to FSGS, are both approximately 7/million/year (Sim et al., 2016). Thus current therapies may be delaying but not preventing, renal failure (Troyanov et al., 2005).

Additional limitations of current therapy include significant morbidity and premature mortality ascribable to the neurologic, metabolic and bone toxicity associated with high dose glucocorticoids, renal toxicity associated with calcineurin inhibitors, and to immunosuppression. There is a need for therapeutic approaches that induce and maintain response in a greater proportion of subjects with less toxicity.

## 1.6. Risk-Benefit Assessment

For subjects with primary FSGS who do not achieve sustained response with immunosuppression, as assessed by reduction in proteinuria there are no effective therapies available. Histologic recurrence in renal transplants is very high, with high levels of proteinuria portending a poor renal prognosis (Besbas et al, 2015). For subjects who do achieve response, the increased risk of infection associated with corticosteroids is a significant concern, as are the metabolic and neurologic toxicities associated with corticosteroids; these toxicities become increasingly concerning for subjects who require continuous treatment to maintain control (corticosteroid/ immunosuppressant dependent) or who experience frequent relapses and require recurrent treatment.

To date, CCX140-B has been well-tolerated in the 7 completed clinical studies with administered doses ranging from 0.05 mg to 15 mg QD for 12 days and 10 mg QD for 52 weeks.

The rationale for exploring this agent in FSGS is strong. Blockade of CCR2 in murine models of FSGS is associated with reduced proteinuria, improved renal function, and more normal histology. In subjects with diabetic nephropathy, treatment with CCX140-B was associated with

rapid and sustained reduction in proteinuria. If similar findings are observed in clinical trials, CCX140-B may comprise a novel podocyte protective agent to reduce morbidity associated with nephrotic syndrome and sustain renal function, with a favorable safety profile compared to current best standards of care.

## 2. OBJECTIVES

### 2.1. Primary Efficacy Objective

The Primary Efficacy Objective is to evaluate the effect of CCX140-B on proteinuria in subjects with primary FSGS with nephrotic syndrome, assessed as a median reduction from baseline of urine protein to creatinine ratio (UPCR) of at least 20%, i.e.  $\geq 20\%$ , by week 12.

### 2.2. Secondary Efficacy Objectives

The secondary efficacy objectives of this study will be assessed at Study Week 12 and through End of Treatment and include:

1. Achievement of partial or complete remission of urine protein to creatinine ratio (UPCR) through Study Week 12 and through the end of treatment, where partial and complete remission are defined as follows:

Partial Remission (includes all of the following)

- reduction from baseline by  $\geq 50$  percent in UPCR
- reduction in UPCR to a level that is  $< 3.5$  g/g
- subject may not be a treatment failure

Complete Remission (includes all of the following)

- reduction in UPCR to  $< 0.3$  g/g
- serum albumin within normal range
- For patients with abnormal serum creatinine levels at baseline, return to normal levels
- For patients with normal serum creatinine levels at baseline, final value within 20% of baseline levels
- subject may not be a treatment failure

2. Assessment of change from baseline in UPCR over time
3. Assessment of time to, and proportion of subjects with achievement of partial remission
4. Assessment of time to, and proportion of subjects with achievement of complete remission
5. Assessment of time to rescue therapy, based on Investigator or physician initiation of glucocorticoids or new immunosuppressive agents or new major treatment modalities (e.g. plasmapheresis, dialysis)

6. Changes over time in other laboratory parameters related to renal function, including:

- Serum albumin
- Creatinine
- Cystatin C
- eGFR, calculated by the CKD-EPI Cystatin C equation, CKD-EPI Creatinine equation, CKD-EPI Creatinine-Cystatin C equation and MDRD Creatinine equation.
- urine albumin to creatinine ratio (UACR)
- total 24 hour urine protein excretion

7. Quality of Life endpoints include:

- Change in factors associated with quality of life from baseline over time as assessed using the SF-36 v2
- Change in factors associated with quality of life from baseline over time as assessed using the EQ-5D-5L

### **2.3. Safety Objectives**

The safety objectives of CCX140-B will be assessed via the following endpoints:

1. Adverse events
2. Vital signs
3. Electrocardiograms
4. AIDS Clinical Trials Group Brief Peripheral Neuropathy Screening Tool (ACTG BPNST):  
To assess potential signs and symptoms of peripheral neuropathy the ACTG BPNST will be completed by study personnel or the study investigator as specified in the Time and Events table.
5. Changes in laboratory parameters including:
  - Hematology including complete blood count, reticulocyte count, smear evaluation
  - Serum haptoglobin, lactate dehydrogenase
  - Serum chemistry including serum transaminases and CPK
  - Urinalysis
  - Coagulation factors (Prothrombin Time [PT], Partial Thromboplastin Time [PTT], International Normalization Ratio [INR])

### **2.4. Exploratory Objectives**

Whole blood, plasma, serum and urine will be collected at baseline and at intervals over the course of the treatment period for exploratory analyses. Parameters will include:

1. Assessment of biomarkers associated with disease activity over time, including blood lipid profile, MCP-1 excreted in urine, and potentially other biomarkers of renal inflammation, fibrosis and injury
2. Assessment of biomarkers associated with risk of severity of disease, which may include allelic variations associated with the pathogenesis and/or prognosis of FSGS such as NPHS1, NPHS2, WT-1, LAMB2, CD2AP, TRPC6, ACTN4, INF2, APOL1

3. Assessment of blood and/or urinary biomarkers associated with CCR2 biology, which may include peripheral blood leukocyte subsets and selected cytokines and chemokines
4. Assessment of mechanisms by which nephrotic syndrome may potentially impact pharmacokinetics of CCX140, including assessment of CCX140 in urine.
5. Assessment of edema as measured by physical examination, leg circumference and body weight
6. Assessment of concentration of CCX140-B in urine

### **3. STUDY DESIGN AND DOSING REGIMEN**

#### **3.1. Initial Treatment Phase**

This is an open label clinical trial to test the efficacy, safety, pharmacokinetics and tolerability of ascending doses of CCX140-B in subjects with primary FSGS and nephrotic syndrome.

The screening period will be up to 28 days. Subjects will visit the study center during Screening and on Day 1 (baseline), weekly throughout Dose Escalation, then every 2 weeks through Study Week 12.

Eligible subjects will start treatment with CCX140-B at 5 mg twice daily. CCX140-B will be taken orally without food, at least one hour before meal. The dose will be increased in a stepwise manner to 15 mg twice daily while monitoring safety, in accordance with the rules ([Table 1](#) and [Figure 1](#)) and schedule detailed in the [Time and Events Table](#). Treatment at the selected dose will be continued up to Week 12 or until declaration of Treatment Failure.

This study incorporates intra-subject dose escalation and dose modification. Four factors guide dose modification including:

1. Time
2. Response
3. Exposure
4. Safety

During the initial 12 weeks of treatment, dose will be escalated from 5 mg twice daily to 10 mg twice daily on Study Day 15, then to 15 mg twice daily on Study Day 43, if subjects are not considered treatment failures and who otherwise meet criteria for continuation ([Table 1](#), [Figure 1](#)).

If planned dose escalation to 10 mg (on day 15) or 15 mg twice daily (on day 43) was previously halted the dose may be escalated further if subjects are not considered treatment failures and who otherwise meet criteria for continuation ([Table 1](#), [Figure 1](#)). In such case the subject will return approximately 2 weeks later for blood draws to assess PK (AUC0-6). Subjects will return 2 weeks after the PK assessment to evaluate the safety and need for further dose adjustment.

At any time during the study dose may be de-escalated for safety, or if projected exposure exceeds the maximum allowable exposure defined for the study. Because exposure may be impacted by changes in proteinuria, the protocol requires assessment of exposure if proteinuria declines significantly.

Blood will be drawn to evaluate trough exposure in accordance with the Time and Events Schedule. In addition, as detailed in [Table 1](#), blood will be drawn to assess exposure (AUC0-12, extrapolated from measured AUC0-6), at the following times to guide dosing decisions:

- Study Day 1 prior to first dose of CCX140, and at intervals through 6 hours following the initial dose
- On study Day 29, two weeks following initiation of 10 mg twice daily, to assess exposure at steady state, and to confirm that exposure is within the safety margins based on non-clinical NOAEL
- If dose was adjusted on Day 43, blood will be collected on study Day 57 to assess exposure
- Additional assessments of exposure may be scheduled if indicated. Indications may include:
  - Subjects receiving a total dose greater than 10 mg daily who have experienced at least 50% reduction in proteinuria since the previous PK assessment, to assess impact of change in proteinuria on exposure and to ensure exposure is within safety margins
  - Subjects who experienced a potentially dose-limiting safety event
  - Subjects who required a dose reduction for higher than planned exposure; PK will be assessed approximately 2 weeks after reduction
  - Subjects for whom dose is adjusted for any other reason; PK will be assessed approximately 2 weeks after reduction

If measured or projected steady state PK exposure (AUC0-12) exceeds 240  $\mu\text{g}\cdot\text{h}/\text{mL}$ , which is approximately half of the rat NOAEL AUC0-24, the dose will be reduced to the dose projected to provide exposure within the target range.

### **3.1.1. Day 85 and Beyond**

If dose is adjusted upward or downward for any reason at Day 85 or during the extended treatment period the subject will return approximately 2 weeks later for blood draws to assess PK (AUC0-6). Subjects will return 2 weeks after the PK assessment to evaluate the safety and need for further dose adjustment.

### **3.1.2. Extended Treatment Period**

Subjects are eligible for the extended treatment period under the following conditions:

- 1) Not considered treatment failures as of Week 12 *and*
- 2) In the opinion of the Investigator, remain candidates for investigational treatment *and*
- 3) Any of the conditions below apply:
  - Partial or Complete Remission by Week 12
  - Response with  $\geq 20\%$  reduction in UPCR by Week 12
  - No longer have nephrotic syndrome

These subjects will return to the clinic for safety, PK and efficacy measurements every 4 weeks. Subjects taking CCX140-B at 15 mg twice daily will be maintained at that dose unless de-escalation is required based on safety signal or steady state PK exposure (AUC0-12) that exceeds 240  $\mu\text{g}\cdot\text{h}/\text{mL}$ .

Subjects can be considered for dose escalation if all of the following are true:

- Subject is not already treated with 15 mg twice daily *and*
- Subject did not require previous downward dose adjustment *and*
- Subject is not a Treatment Failure, *and*
- Meets all criteria for continuation:
  - Subject has not achieved and maintained at least a Partial Remission, *and*
  - Projected AUC0-12 on the next higher planned dose level does not exceed 240  $\mu\text{g}\cdot\text{h}/\text{mL}$  *and*
  - The next higher dose does not exceed the Maximum Tolerated Dose (MTD)

Subjects who undergo dose escalation will return to clinic approximately 2 weeks after initiation of the increase for assessment of PK.

Dose modification rules that applied during the initial dose escalation period also apply to dose escalation after 12 weeks.

### 3.1.3. Follow-Up

Following completion of treatment, or early termination of treatment, all subjects should be urged to return for the termination visit and again 7 and 14 days after their last dose for blood draws to assess elimination pharmacokinetics, and 28 days after their last dose for follow-up and End of Study visit assessments. Appropriate standard of care medical treatment should be provided to all subjects as needed.

After Study Day 43, dose escalation can occur by not more than one step monthly. Within 2 weeks following each dose escalation, PK must be assessed to ensure that the projected AUC0-12 does not exceed 240  $\mu\text{g}\cdot\text{h}/\text{mL}$ . Unscheduled visits for assessment of PK may be required.

Stopping rules and dose reduction rules that applied during the 12 week initial dose escalation period also apply during dose escalation after 12 weeks (See [Table 2](#)).

Throughout the treatment period, any changes in background medications should be limited to settings in which the Investigator deems it to be necessary for the safety of the subject.

Subjects will be discharged from the study when all the visit procedures have been completed.

## 3.2. Dose Modification Based on PK Exposure

Blood will be drawn to evaluate trough exposure in accordance with the Time and Events Schedule. In addition, blood will be drawn to assess exposure (AUC0-12, extrapolated from measured AUC0-6) at the following times to guide dosing decisions:

- Study Day 1 prior to first dose of CCX140-B, and at intervals through 6 hours following the initial dose
- Two weeks (Day 29) following initiation of 10 mg twice daily, to assess exposure at steady state, and to confirm that exposure is within the safety margins based on non-clinical NOAEL
- Approximately 2 weeks following initiation of 15 mg twice daily (Day 57, if dose was increased at Day 43), to assess exposure at steady state, and to confirm that exposure is

within the safety margins (projected  $AUC_{0-12}$  less than or equal to 240  $\mu\text{g}\cdot\text{h}/\text{mL}$ ) based on non-clinical NOAEL

- At Study Day 85 PK will be assessed to guide dosing beyond Week 12.
- Additional assessments of exposure may be scheduled if indicated. Indications may include:
  - Subjects receiving a total dose greater than 10 mg daily who have experienced at least 50% reduction in proteinuria since the previous PK assessment, to assess impact of change in proteinuria on exposure and to ensure exposure is within safety margins
  - Subjects who experienced a potentially dose-limiting safety event
  - Subjects who required a dose reduction for higher than planned exposure; PK will be assessed approximately 2 weeks after reduction
  - Subjects for whom dose is adjusted for any other reason; PK will be assessed approximately 2 weeks after reduction

If planned dose escalation to 10 mg (on day 15) or 15 mg twice daily (on day 43) was previously halted the dose may be escalated further if subjects are not considered treatment failures and otherwise meet criteria for continuation ([Table 1](#), [Figure 1](#)). In such cases the subject will return approximately 2 weeks later for blood draws to assess PK ( $AUC_{0-6}$ ). Subjects will return 2 weeks after the PK assessment to evaluate the safety and need for further dose adjustment.

### **3.3. Dose Modifications During the Extended Treatment Period**

If measured or projected exposure steady state PK exposure ( $AUC_{0-12}$ ) exceeds 240  $\mu\text{g}\cdot\text{h}/\text{mL}$ , which is approximately half of the rat NOAEL  $AUC_{0-24}$ , the dose will be reduced to the dose projected to provide exposure within the target range.

For subjects who escalate dose to 10 mg twice daily on Study Day 15, PK samples from the dose two weeks after 10 mg BID dosing (planned for Day 29) will be analyzed expeditiously and the PK data will be used for projecting the steady state PK exposure. If the projected steady state PK exposure ( $AUC_{0-12}$ ) is higher than 240  $\mu\text{g}\cdot\text{h}/\text{mL}$ , which is half of the rat NOAEL steady state  $AUC_{0-24}$ , the dose will be reduced to 5 mg BID for the remainder of the study ([Table 2](#)).

If the projected steady state PK exposure ( $AUC_{0-12}$ ) is lower than 240  $\mu\text{g}\cdot\text{h}/\text{mL}$ , the steady PK exposure at 15 mg BID will be projected from the 10 mg BID Day 43 PK data. If the projected PK exposure ( $AUC_{0-12}$ ) at 15 BID is lower than 240  $\mu\text{g}\cdot\text{h}/\text{mL}$ , the dose will be escalated to 15 BID. If the projected PK exposure ( $AUC_{0-12}$ ) is higher than 240  $\mu\text{g}\cdot\text{h}/\text{mL}$ , the dose will not escalate to 15 mg BID but will stay at 10 mg BID for the remainder of the study.

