**Table 1: Dose Modification Schedule and Rules Through Study Day 85**

Study Day	Dose and Requirements for Dose Modification
1	Initiate dosing at 5 mg twice daily
15	At Day 15, dose will be increased to 10 mg twice daily if all of the following are true: 
 
• Subject has not achieved and maintained at least Partial Remission and
 
• Subject is not a Treatment Failure
 

29	At Day 29, PK samples will be collected to measure AUC 0-6 and enable projection of AUC 0-12 at both the current dose level and the next higher planned dose level AUC 0-12
43	At Day 43 based on results of the Day 29 PK, the dose may be adjusted to the next higher planned dose level (15 mg twice daily for subjects receiving 10 mg twice daily; 10 mg twice daily for subjects receiving 5 mg twice daily) if all of the following are true: 
 
• Subject is not a Treatment Failure, and
 
• Meets all criteria for continuation:               
 
○ Subject has not achieved and maintained at least a Partial Remission, and
 
○ Projected AUC0-12 on the next higher planned dose level does not exceed 240 <math>\mu\text{g}\cdot\text{h}/\text{mL}</math> and
 
○ The next higher dose does not exceed the Maximum Tolerated Dose (MTD)
 
 
 
 NOTE: If the projected AUC 0-12 on the current dose exceeds 240 $\mu\text{g}\cdot\text{h}/\text{mL}$ , dose will be de-escalated to the next lower dose level
57	At Day 57, PK samples will be collected to measure AUC 0-6 and enable projection of AUC 0-12
Day 71	Based on results of Day 57 PK, subjects can be considered for dose escalation if all of the following are true: 
 
• Subject is not already treated with 15 mg twice daily and
 
• Subject did not require previous downward dose adjustment and
 
• Subject is not a Treatment Failure, and
 
• Meets all criteria for continuation:               
 
○ Subject has not achieved and maintained at least a Partial
 
 
 

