#### **6.5. Study Day 43- evaluate results from Day 29 (modify dose per dose modification guidelines based on PK results)**

1. Symptom directed abbreviated physical examination and Vital Signs including weight, heart rate, respiratory rate and body temperature. AIDS Clinical Trials Group Brief Peripheral Neuropathy Screening Tool (ACTG BPNST)
2. First morning void for UPCR measurement
3. Review diary and used study medication with each subject. Confirm dosing compliance.
4. Pharmacokinetics ( $C_{min}$ ) – sample is to be collected at time 0 (just prior to taking the next)

5. Dispense diaries and *Directions for Use* along with CCX140-B bottles. Discuss new potential dose when relevant.
6. Concomitant medications- verify and document any new medications that subject has started since the previous visit.
7. Adverse Events- record all adverse events.

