### 2.3.4 *Pharmacokinetic Endpoints*

Concentrations of CCX140 will be determined in plasma from 4.0-mL blood samples collected in K2EDTA tubes according to Table 1. The following parameters will be determined, where possible:

- Cmax Maximum plasma concentration
- Tmax Time of maximum plasma concentration
- AUC0-6 Area under the plasma concentration-time curve from Time 0 to Hour 6 on Day 1, Day 29 (or Day 14 following 10 mg BID dosing), and Day 57 (or Day 14 following 15 mg BID dosing)
- AUC0-12 Area under the plasma concentration-time curve from Time 0 to Hour 12 on Day 29 (or Day 14 following 10 mg BID dosing), and Day 57 (or Day 14 following 15 mg BID dosing) with the assumption of the concentration of Time 0 being equivalent to Hour 12.
- Cmin Trough level plasma concentrations at Day 57 visit or beyond

On Days 1, 29 and 57, samples will be taken at pre-dose, 0.5, 1, 2, 3, 4, and 6 hours after dosing. The blood samples collected on the other relevant study days need to be collected prior to taking the CCX140-B dose.

Total plasma concentrations of CCX140 will be determined using validated analytical methods.

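### Protocol Section 3.3 projects 15 mg BID exposure from a Day 43 trough that cannot give an AUC, and makes a 10 mg BID exposure hold permanent where Table 1 and other sections allow review

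*Protocol*

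**What the plan says.** **Which sample drives the projection.** Protocol Section 3.3 first checks current exposure on 10 mg BID: "PK samples from the dose two weeks after 10 mg BID dosing (planned for Day 29) will be analyzed expeditiously". Its next paragraph then says that exposure at 15 mg BID "will be projected from the 10 mg BID Day 43 PK data". Table 1 reads differently: "At Day 43 based on results of the Day 29 PK, the dose may be adjusted to the next higher planned dose level". The heading of Section 6.5 agrees with Table 1, telling the site to "evaluate results from Day 29 (modify dose per dose modification guidelines based on PK results".

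**What is collected on Day 43.** Section 6.5, item 4, lists one Cmin draw, worded as "sample is to be collected at time 0 (just prior to taking the next" (the item ends there). The Time and Events Table likewise shows a Cmin and no AUC on Day 43. SAP Section 2.3.4 defines AUC0-12 as "Area under the plasma concentration-time curve from Time 0 to Hour 12 on Day 29 (or Day 14 following 10 mg BID dosing", or on Day 57 or 14 days after 15 mg BID. It names Days 1, 29 and 57 for serial sampling and adds: "The blood samples collected on the other relevant study days need to be collected prior to taking the CCX140-B dose".

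**How long a hold lasts.** If the projected AUC0-12 at 15 mg BID is above 240 µg·h/mL, Section 3.3 says "the dose will not escalate to 15 mg BID but will stay at 10 mg BID for the remainder of the study". The Day 71 row of Table 1 lets a subject not yet on 15 mg BID be considered for escalation on the Day 57 PK, with the 240 test among the criteria. Its only bar based on dosing history is a previous downward adjustment. The synopsis and Sections 3.1 and 3.2 allow a halted escalation to be resumed, and the synopsis extension rules and Section 3.1.2 allow escalation to be considered in the extension. The text of the SAP study schematic does the same. SAP Section 2.2.3 refers the reader to both Section 3 and Table 1 of the protocol.

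**The concern.** The 240 µg·h/mL limit is the trial's exposure-safety ceiling, so the rule applying it should name a sample from which exposure can be calculated. Section 3.3 names one that does not fit the protocol's stated method. A site that improvised from the trough would be using a figure that tends to understate AUC, against a safety limit.

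On permanence, a subject held at 10 mg BID for projected exposure stays there under Section 3.3, but may be reviewed on Day 71 and in the extension under Table 1. Two sites could therefore dose the same subject differently, each with a protocol section in support, and the dose received would depend partly on which section was read.

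**Working it through.** **1. The ceiling.** Section 3.3 calls 240 µg·h/mL about half the rat NOAEL AUC0-24. Section 1.3 gives 464.6 (males) and 493.7 (females):
- 464.6 / 2 = 232.3 and 493.7 / 2 = 246.9; their mean is 239.6. The stated 240 reproduces, so the ceiling itself is not in question.

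**2. Can the Day 43 sample give the projection?**
- Day 29 (Section 6.4): 0, 0.5, 1, 2, 3, 4 and 6 h = 7 time points.
- Day 43 (Section 6.5): time 0 only = 1 time point.
- Sections 3.1 and 3.2 extrapolate AUC0-12 from a measured AUC0-6. The SAP's assumption that the pre-dose level equals the 12 h level (Sections 2.3.4 and 3.5) supplies the last point of the curve but still needs the 0–6 h series. One trough gives no AUC0-6.
- Time to the decision: 43 − 29 = 14 days for a Day 29 sample; 43 − 43 = 0 days for a Day 43 sample.
- A trough multiplied by 12 h is only a lower bound. On the projected 15 mg BID trough (about 5.5 µg/mL, Section 5.2.1), 5.5 × 12 = 66 against the projected AUC0-12 of 72, or 8% low. The shortfall grows with the peak-to-trough swing. If trough × 12 were 120 on 10 mg BID, the 15 mg BID projection would be 180, 216 or 270 for an average-to-trough ratio of 1.0, 1.2 or 1.5 (assumed range), on either side of 240.

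**3. When does a hold arise?** Assume dose-proportional kinetics.
- Projected AUC0-12 on 10 mg BID without proteinuria: 72 × 10/15 = 48.
- AUC0-12 on 10 mg BID that projects to 240 at 15 mg BID: 240 × 10/15 = 160.
- Above 240 on 10 mg BID, Section 3.3 reduces the dose instead, so the hold applies between 160 and 240.
- Trigger relative to projection: 160 / 48 = 3.3.
- The synopsis reports lower exposure in diabetic nephropathy subjects with 2–3 g albuminuria, stated as about 30% lower (0.8 versus 1.2 µg/mL is 33%). Applied as an illustration: 48 × 0.70 = 33.6 and 160 / 33.6 = 4.8; 48 × (0.8/1.2) = 32 and 160 / 32 = 5.0.

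**4. When do the two rules then give different doses?** Only if a held subject's AUC0-12 later falls to 160 or below on the same dose, without remission.
- For a subject with no dose increase, the only later AUC in the Time and Events Table is Day 57. Section 3.2 also lists Day 85, and unscheduled assessments are possible.
- Section 3.1.3 limits escalation after Day 43 to one step a month. The last step would have been Day 15, and 71 − 15 = 56 days, so that limit does not block a Day 71 escalation.
- If the fall occurred, doses could differ for 85 − 71 = 14 days before Day 85, and for up to 365 − 71 = 294 days if the subject entered the extension.

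**5. A rule that does not conflict.** Section 3.3 also keeps a subject reduced to 5 mg BID at that dose. This agrees with Table 1, which bars escalation after a downward adjustment. The conflict is confined to the hold at 10 mg BID.

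**The case against.** **The Day 43 reference is a slip.** Table 1, the Section 6.5 heading and the preceding paragraph of Section 3.3 all point to Day 29, so a reader can work out what was probably meant. That is likely, but the sentence is current text stating an escalation rule. Two possible rescues fail. Footnote 7 of the Time and Events Table asks for serial samples on the relevant day for each escalation, but the table and Section 6.5 give Day 43 a Cmin only. A population PK model could use a trough, but Section 8.11 plans one only if the data suffice and nothing ties it to dosing.

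**The other sections are permissive.** They say that escalation may resume or can be considered, so Section 3.3 could be read as the specific rule for exposure holds, and a site obeying it breaches nothing. This stands in part: it is a question of precedence that the protocol leaves open. However, one of the permissions is in Section 3.2, the section on PK-based dose modification. Projected exposure is also an express Day 43 criterion in Table 1, and no section excludes exposure holds from later review.

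**The 294 days is remote.** It needs AUC to fall while the subject qualifies for the extension without remission. The protocol expects exposure to be lower with heavier proteinuria, so improving proteinuria would tend to raise AUC. These conditions pull against each other, and the figure is an outer bound only.

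**Conclusion.** The point holds and is minor. The Day 43 sample named in Section 3.3 cannot give the AUC that the rule needs under the protocol's own method: one time point against seven. The permanence of a 10 mg BID exposure hold in Section 3.3 is not reconciled with the later review allowed by Table 1, the synopsis and Sections 3.1, 3.1.2 and 3.2.

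The practical effect is small. A hold requires exposure 3.3 to 5.0 times the projected level, assuming dose proportionality and, for the upper figure, an illustrative reduction for proteinuria. At most 13 subjects could be affected. SAP Section 1 says enrolment was not continued, and SAP Sections 3.1.5 and 6 make the efficacy analysis descriptive, so no test result depends on this. This review does not say which dosing rule is right.

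**What to change.** Reconcile Section 3.3 with Table 1, Sections 3.1, 3.1.2, 3.2 and 6.5, the synopsis and the SAP schematic on two points:
- name one PK sample able to give AUC0-6 for the 15 mg BID projection;
- give an exposure-based hold at 10 mg BID the same status, permanent or reviewable, in every section.

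While the text is open, align the down-titration bar. Table 1 refers to any earlier reduction, whereas the SAP schematic text refers to a reduction from 15 mg BID. The Day 57 AUC could also be worded the same way in the schedule and in the text, although sampling everyone already satisfies the conditional wording.

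If no amendment is feasible, record in the CSR which rule was applied and whether any subject was held for exposure. The sponsor decides the rule; no dose or cap is proposed here.

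The cost is wording changes in the protocol and SAP schematic, or one CSR note. No subjects or samples are added, because the Day 29 and Day 57 series are already scheduled.
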